Survival Status		X	
Per Protocol Amendment 01, survival follow-up will stop after the second safety assessment (FU2) at 100 days.
 
The following information is no longer applicable per Protocol Amendment 01 and refers to the original study design.
 
During safety follow-up and every 3 months (may be accomplished by clinic visit or by telephone contact) during the survival Follow-up Period. Include documentation of subsequent chemotherapy.

Abbreviations: AE = adverse event; BP = blood pressure; BMS = Bristol-Myers Squibb; CT = computed tomography; ECOG = Eastern Cooperative Oncology Group; eCRF = electronic case report form; EQ-5D-5L = EuroQol-5 Dimensions-5 Levels; FACT-Hep = Functional Assessment of Cancer Therapy-Hepatobiliary; FU1 = follow-up visit 1; FU2 = follow-up visit 2; HCG = human chorionic gonadotropin; HCRU = healthcare resource utilization; IMG = immunogenicity; IU = international unit; L = liter; MRI = magnetic resonance imaging; NCI CTCAE = National Cancer Institute Common Terminology Criteria for Adverse Events; PE = physical examination; PK = pharmacokinetic; PS = performance status; RNA = ribonucleic acid; SAE = serious adverse event; SARS-CoV-2 = severe acute respiratory syndrome coronavirus 2; SOC = standard of care; WOCBP = women of childbearing potential.

^a Participants must be followed for at least 100 days after last dose of study treatment. FU1 should occur 30 days from the last dose (± 7 days) or can be performed on the date of discontinuation if that date is great than 42 days from the last dose. FU2 occurs approximately 100 days (± 7 days) from last dose of study treatment. Both follow-up visits should be conducted in person.

^b **Not applicable per Protocol Amendment 01.** The following information refers to the original study design. Survival Follow-up visits to occur every 12 weeks (± 14 days) from FU2. Survival visit may be conducted in person or by telephone. BMS may request that survival data be collected on all treated participants outside of the 3 month specified window. At the time of this request, each participant will be contacted to determine their survival status unless the participant has withdrawn consent for all contact.

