5.5.1 Nivolumab Clinical Pharmacology Summary

The PK of nivolumab were studied in participants over a dose range of 0.1 to 10 mg/kg, administered as a single dose or as multiple doses of nivolumab every 2 or 3 weeks. The geometric mean (coefficient of variation [%CV], %) CL was 9.5 mL/h (49.7%), geometric mean volume of distribution at steady state (V_{ss}) was 8.0 L (30.4%), and geometric mean elimination half-life (t_{1/2}) was 26.7 days (101%). Steady-state concentrations of nivolumab were reached by 12 weeks when administered at 3 mg/kg Q2W, and systemic accumulation was approximately 3-fold. The exposure to nivolumab increased dose-proportionally over the dose range of 0.1 to 10 mg/kg administered Q2W. The CL of nivolumab increased with increasing body weight. The PPK analysis suggested that the following factors had no clinically important effect on the CL of nivolumab: age (29 to 87 years), gender, race, baseline lactate dehydrogenase (LDH), and PD-L1. A PPK analysis suggested no difference in CL of nivolumab based on age, gender, race, tumor type, baseline tumor size, and hepatic impairment.

Although ECOG performance status, baseline glomerular filtration rate (GFR), albumin, and body weight had an effect on nivolumab CL, the effect was not clinically meaningful. When nivolumab was administered in combination with ipilimumab, the CL of nivolumab was increased by 24%, whereas there was no effect on the CL of ipilimumab. Additionally, PPK and E-R analyses have been performed to support use of 240-mg Q2W dosing in addition to the 3 mg/kg Q2W regimen. Using the PPK model, exposure of nivolumab at a 240-mg flat dose was identical to a dose of 3 mg/kg for participants weighing 80 kg, which was the approximate median body weight in nivolumab clinical trials.

Full details on the clinical pharmacology aspects of nivolumab can be found in the IB.¹

5.5.2 ***Ipilimumab Clinical Pharmacology Summary***

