- ii) Either a FFPE tissue block (preferred) or a minimum of 20 unstained slides of tumor tissue sections obtained within 3 months prior to randomization or archived (if above is not available) with an associated pathology report must be submitted to the central laboratory for inclusion. The central laboratory must provide IRT with confirmation of receipt of evaluable tumor tissue prior to randomization. Biopsy should be excisional, incisional or core needle. Fine needle aspiration or other cytology samples are unacceptable for submission. If despite best efforts, a minimum of 20 slides are not obtainable, submission of fewer slides may be acceptable in some circumstances following discussion with BMS Medical Monitor or Clinical Scientist. Please see [Appendix 9](#) for country-specific criteria for the collection of tumor tissue samples in China.
- d) Participant has cirrhotic status of Child-Pugh Class A (refer to [Appendix 8](#)).
- e) Participant has an Eastern Cooperative Oncology Group (ECOG) PS of 0 or 1 (refer to [Appendix 5](#) for ECOG PS scale).
- f) Participants are eligible to enroll if they have non-viral related HCC, or if they have HBV-HCC, or HCV-HCC defined as follows:
- i) Non-HBV, non-HCV related HCC
- ii) HBV-HCC
- (1) Resolved HBV infection, as evidenced by detectable HBV surface antibody, detectable HBV core antibody, undetectable HBV deoxyribonucleic acid (DNA), and undetectable HBV surface antigen [HBsAg]); OR
- (2) Chronic HBV infection, as evidenced by detectable HBsAg or HBV DNA. Participants with chronic HBV infection must be on antiviral therapy [REDACTED]

iii) HCV-HCC

- (1) Resolved HCV infection as evidenced by detectable antibody; OR
- (2) Chronic HCV infection as evidenced by detectable HCV ribonucleic acid (RNA).

3) Age and Reproductive Status

- a) Males and Females, ages ≥ 18 years or age of majority.
- b) WOCBP must have a negative serum or urine pregnancy test (minimum sensitivity 25 IU/L or equivalent units of human chorionic gonadotropin [HCG]) within 24 hours prior to the start of study treatment.
- c) Women must not be breastfeeding.
- d) WOCBP must agree to follow instructions for method(s) of contraception for the duration of treatment with study treatments plus approximately 5 half-lives of the study treatments plus 30 days (duration of ovulatory cycle) for a total of 5 months post-treatment completion.

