9.2.2 Time Period and Frequency for Collecting AE and SAE Information

All non-serious AEs (not only those deemed to be treatment-related) should be collected continuously during the treatment period and for a minimum of 100 days following discontinuation of dosing, at the timepoints specified in [Section 2](#) (Schedule of Activities).

All SAEs must be collected from the time of signing the consent, including those thought to be associated with protocol-specified procedures and for a minimum of 100 days of discontinuation of dosing. For participants randomized/assigned to treatment and never treated with study drug, SAEs should be collected for 30 days from the date of randomization.

All AEs (SAEs and non-serious AEs) associated with confirmed or suspected SARS-CoV-2 infection must be collected from the time of signing the consent until 100 days following discontinuation of dosing.

The Investigator must report any SAE that occurs after these time periods and that is believed to be related to study drug or protocol-specified procedure (eg, a follow-up skin biopsy).

- Medical occurrences that begin before the start of study treatment but after obtaining informed consent will be recorded on the appropriate section of the eCRF module.
- All SAEs will be recorded and reported to the Sponsor or designee within 24 hours, as indicated in [Appendix 3](#).
- The Investigator will submit any updated SAE data to the Sponsor or designee within 24 hours of the updated information being available.

Investigators are not obligated to actively seek AEs or SAEs in former study participants. However, if the Investigator learns of any SAE, including a death, at any time after a participant has been discharged from the study, and he/she considers the event reasonably related to the study treatment or study participation, the Investigator must promptly notify the Sponsor.

The method of evaluating and assessing causality of AEs and SAEs and the procedures for completing and reporting/transmitting SAE reports are provided in [Appendix 3](#).

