9.2.6 Pregnancy

If, following initiation of the study treatment, it is subsequently discovered that a participant is pregnant or may have been pregnant at the time of study exposure, including during at least 5 half-lives after product administration, the Investigator must immediately notify the BMS Medical Monitor/Clinical Scientist of this event and complete and forward a Pregnancy Surveillance Form to the BMS Designee within 24 hours of awareness of the event, and in accordance with SAE reporting procedures described in [Appendix 3](#).

If the Investigator determines a possible favorable benefit-risk ratio that warrants continuation of study treatment, or re-initiation of study treatment, a discussion between the Investigator and the BMS Medical Monitor/Clinical Scientist must occur. If, for whatever reason, the pregnancy has ended, confirmed by negative serum pregnancy test, treatment may be resumed (at least 3 weeks and not greater than 6 weeks after the pregnancy has ended), following approvals of participant/Sponsor/IRB/EC, as applicable. Study treatment must be permanently discontinued where locally mandated; see [Appendix 9](#) for country-specific requirements.

Follow-up information regarding the course of the pregnancy, including perinatal and neonatal outcome and, where applicable, offspring information must be reported on the Pregnancy Surveillance Form.

Any pregnancy that occurs in a female partner of a male study participant should be reported to the Sponsor or designee. In order for the Sponsor or designee to collect any pregnancy surveillance information from the female partner, the female partner must sign an ICF for disclosure of this information. Information on this pregnancy will be collected on the Pregnancy Surveillance Form.

In cases where a study drug can be present in seminal fluid, at exposures sufficient to potentially cause fetal toxicity, and if any sexual activity (eg, vaginal, anal, oral) has occurred between a male participant and a pregnant WOCBP partner(s), the information should be reported to the Sponsor or designee, even if the male participant has undergone a successful vasectomy. In order for the Sponsor or designee to collect any pregnancy surveillance information from the female partner,

the female partner(s) must sign an ICF for disclosure of this information. Information on the pregnancy will be collected on the Pregnancy Surveillance Form.

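### FU2 may be held from day 93 and, since Amendment 01, no scheduled contact follows it, so up to 7 days of the stated 100-day minimum can lack a timepoint for detecting new adverse events

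*Combined protocol and SAP*

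**What the plan says.** Table 2-3, footnote a, sets two rules side by side. The first is a minimum: "Participants must be followed for at least 100 days after last dose of study treatment". The second is the visit window: "FU2 occurs approximately 100 days (± 7 days) from last dose of study treatment".

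The 100-day period appears in several other places. Section 9.2.2 requires non-serious AEs to be collected "for a minimum of 100 days following discontinuation of dosing", at the timepoints given in Section 2, and sets the same minimum for SAEs. Section 5.1.3 gives the same minimum for documenting toxicities. Section 8.1.3, in text written for Amendment 01, runs safety follow-up through day 100.

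Amendment 01 ends the visits after FU2. The Survival Status row of Table 2-3 says "survival follow-up will stop after the second safety assessment (FU2) at 100 days". Footnote b marks the 12-weekly survival visits as not applicable, and footnote c of Figure 5.1-1 confirms that none will occur. The AE row of Table 2-3 is still ticked in the survival-visit column.

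For FU1, footnote a allows 30 days ± 7 days from the last dose, or says the visit "can be performed on the date of discontinuation if that date is great than 42 days from the last dose".

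**The concern.** A site can keep to the FU2 window and still have no scheduled occasion to meet the 100-day minimum. In the original design this did little harm, because AEs were also to be recorded at the survival visits, and an event missed after an early FU2 could be picked up there. Amendment 01 removed those visits and did not adjust the window.

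At stake is completeness of the one objective left in Section 4: the incidence of AEs, SAEs, deaths, AEs leading to discontinuation and laboratory abnormalities. If some participants are last asked about events on day 93 and others on day 107, the effective ascertainment period depends on the appointment date and can be shorter than the stated minimum. Events well after the last dose are a real possibility: Section 3.2.8 describes a death attributed to study drug 79 days after the last dose. That event would have preceded even an early FU2, so it shows only that a long post-dose window has a purpose.

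**Working it through.** The 100-day minimum is a rule, so there is no derived figure to reproduce. The check is day arithmetic, counting from the last dose.

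**Inputs**
- Minimum follow-up and AE collection: 100 days (Table 2-3 footnote a; Sections 5.1.3, 8.1.3, 9.2.2).
- FU2: 100 ± 7 days (footnote a).
- Original survival visits: every 12 weeks (84 days) ± 14 days from FU2 (footnote b), now not applicable.
- FU1: 30 ± 7 days, or the discontinuation date if that is more than 42 days after the last dose (footnote a).

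**FU2 window**
- Earliest: 100 − 7 = day 93. Latest: 100 + 7 = day 107.
- Permitted days: 107 − 93 + 1 = 15.
- Days before day 100: 93 to 99, which is 7 of the 15. This counts calendar days. The documents give no distribution of visit dates, so it is not a proportion of participants.

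**Uncovered days when FU2 is on day d < 100**
- Shortfall = 100 − d.
- d = 93 gives 7 days; d = 99 gives 1 day.

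**Next scheduled contact**
- Original design, all permitted FU2 dates: from 93 + 84 − 14 = day 163 to 107 + 84 + 14 = day 205, with the AE row ticked.
- Under Amendment 01: none.

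**After the change**
- With FU2 at 100 days (+7 days), the window is days 100 to 107 and the shortfall is 0.

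**FU1**
- First branch: 30 − 7 = day 23 to 30 + 7 = day 37.
- Second branch: day 43 onward.
- Uncovered: days 38 to 42, which is 5 days.
- The case can arise. Section 8.1.1.1 makes a dosing delay a reason for discontinuation only beyond 8 weeks (56 days) from the previous dose, so a participant on hold may be taken off treatment on days 38 to 42.

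**The case against.** The strongest reply is that collection does not depend on the visit. The 100-day duty is stated several times and Amendment 01 does not shorten it. The AE row of Table 2-3 asks for continuous collection. Section 5.1.3 keeps participants with ongoing treatment-related AEs under follow-up after FU2. Section 9.2.4 follows SAEs until they resolve, stabilize or are otherwise accounted for. Section 9.2.2 requires related SAEs to be reported even after the period ends. A diligent site would telephone.

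Most of this stands, and it limits the point. A reader might infer that Amendment 01 ends every contact after FU2, or that AE capture closes on day 93. The documents do not say so: what stops at FU2 is survival follow-up. The reply does not supply a timepoint, however. Section 9.2.2 itself refers non-serious AEs to the Section 2 schedule, which offers nothing between an early FU2 and day 100. The duties that continue concern events already known, or SAEs believed related. Section 5.3 also defines the end of trial by the last participant's last visit or scheduled procedure, so an early final FU2 could place it before day 100.

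A reader might also infer that pregnancy surveillance is cut short. Section 9.2.6 covers exposure "including during at least 5 half-lives after product administration", which at the 26.7-day nivolumab half-life in Section 5.5.1 is 5 × 26.7 = 133.5 days, and contraception for women runs "for a total of 5 months post-treatment completion", about 152 days. The documents do not support that reading as a consequence of the window or of the amendment:
- Section 9.2.6 is a reporting duty triggered by discovery, and the contraception periods are obligations on participants.
- Pregnancy tests were scheduled at FU1 and FU2 and never at survival visits.
- The first survival visit would have come on day 163 at the earliest, after both periods.
- Even an FU2 on day 107 precedes day 133.5 by 26.5 days, so the ± 7 days is not the cause.

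On FU1, the second branch is permissive, Section 7.4.2 calls for weekly re-evaluation during a delay, and no loss of data is shown.

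**Conclusion.** The point holds in a narrow form. Footnote a states a 100-day minimum and a visit window that opens on day 93, and Amendment 01 removed the only later scheduled visits at which AEs were to be recorded. A participant seen on days 93 to 99 has 1 to 7 days of the minimum with no scheduled timepoint. The exposure is to new-onset events, mainly non-serious or unrelated ones. The duty to collect remains in force.

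The size is modest: at most 7 days per participant, with 26 randomized as of 14-Oct-2021. The effect on the reported safety results cannot be established, because Section 10.3.2 leaves the safety analyses to the SAP and the available text does not give their reporting window. It is worth correcting because the inconsistency is plain and safety is the sole objective.

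This rests on three assumptions: that the last dose and discontinuation of dosing are the same date; that the tick in the AE row under survival visits has no effect once those visits are void; and that no unscheduled contact happens to fall after FU2. The FU1 gap is real but minor.

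**What to change.** Change the FU2 window in footnote a to 100 days (+7 days). Alternatively, keep ± 7 days and require one telephone contact for AEs, SAEs and vital status on or after day 100 whenever FU2 was held earlier. The call would be in addition to the in-person visit that footnote a already requires. Remove the tick for AE assessment in the void survival-visit column at the same time.

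The cost is footnote wording. Some FU2 visits would fall up to a week later, or some participants would need one extra call.

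Separately, reconcile the two FU1 branches so that they meet. The documents do not show whether the 42-day figure or the ± 7-day window is the misfit, so the sponsor should settle which to change. No additional pregnancy contacts are proposed.

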3 INTRODUCTION

3.1 Study Rationale

Nivolumab is currently in development and has been registered in a variety of tumors.¹ Development of nivolumab for hepatocellular carcinoma (HCC) was initiated in 2012 with CA209040, which is a Phase 1/2 clinical trial evaluating the safety and efficacy of nivolumab in advanced² Data from the dose-escalation and expansion cohorts of this study led to the approval of nivolumab for the second-line (2L) therapy of advanced HCC patients who progressed on or were intolerant to sorafenib.

Combining immunotherapeutic agents with different mechanisms of action offers the possibility of an additive to synergistic response, and therefore represents an attractive therapeutic option that has proven to be effective in several cancer types¹ In advanced HCC, data from CA209040 shows promising results of the combination nivolumab and ipilimumab as 2L therapy, with durable antitumor activity and an acceptable and manageable safety profile and led to the Food and Drug Administration (FDA) accelerated approval of nivolumab in combination with ipilimumab for the treatment of HCC patients who have been previously treated with sorafenib.³ These data provide support for evaluation of nivolumab and nivolumab and ipilimumab in an earlier stage of HCC (ie, intermediate-stage HCC).

3.1.1 Research Hypothesis

Not applicable per Protocol Amendment 01. The following information refers to the original study design.

Treatment with nivolumab and ipilimumab or nivolumab in combination with trans-arterial chemoembolization (TACE) will improve time to TACE progression (TTTP) and/or overall survival (OS) compared to TACE in participants with intermediate stage HCC.

3.1.2 Changes Per Protocol Amendment 01

 Therefore, a decision was made by Bristol-Myers Squibb (BMS) in September 2021 to stop the study. Importantly, there is no change to the understanding of the safety profile of nivolumab alone or in combination with ipilimumab and TACE for the treatment of patients with intermediate-stage HCC.

As of 22-Sep-2021, the following measures were put into effect:

- Enrollment of new participants was closed.
- Participants who signed study consent prior to this notification and were undergoing screening were permitted to be randomized to study treatment.
- Participants currently on treatment were allowed to continue study treatment.

- For participants currently in survival follow-up, it is at the discretion of the investigator and participant whether to continue follow-up until Protocol Amendment 01 is approved by the relevant Health Authorities and Institutional Review Boards (IRBs)/Independent Ethics Committees (IECs) at the site.

Protocol Amendment 01 describes the modification to study procedures. All participants must be re-consented upon approval and implementation of Protocol Amendment 01. These changes affect all participants and should be implemented when Protocol Amendment 01 is implemented at the site.

Key changes in Protocol Amendment 01 include:

- Details of closure of the study, with provision for participants currently on treatment or in the follow-up period to continue in the study per the current protocol amendment.
- The study will be unblinded.
- Removal of placebo infusions for participants in Arms B and C.
- Removal of pharmacokinetic (PK), immunogenicity (IMG), biomarker, and patient-reported outcome (PRO) assessments. **Only safety assessments will be conducted.**
- Removal of on-study imaging assessments. Sites should continue imaging assessments per local standard of care.
- Removal of study-related efficacy assessments. Sites should continue efficacy assessments per local standard of care.
- Align dose modification criteria and immuno-oncology agent management algorithms with the current National Cancer Institute (NCI) Common Terminology Criteria for Adverse Events (CTCAE) version 5.0.
- Add the collection of severe acute respiratory syndrome coronavirus 2 (SARS-CoV-2) infection-related adverse events (AEs) and serious adverse events (SAEs) to evaluate the impact of SARS-CoV-2 on participant safety and add coronavirus disease 2019 (COVID-19) vaccine information for study participants.
- Incorporate country-specific information for France, Czech Republic, and China; incorporate additional updates to improve alignment across protocol sections and/or clarify expectations for assessments, sample collections, and treatment administration.

Changes instituted in Protocol Amendment 01 should override any existing protocol requirements in the event of any apparent discrepancies.

3.2 Background

3.2.1 *The Unmet Need in Intermediate-Stage Hepatocellular Carcinoma*

HCC is the seventh most common cancer in the world and the third most common cause of cancer-related death. There are more than 800,000 new cases a year and HCC causes approximately 700,000 to 800,000 deaths annually. Furthermore, its incidence and prevalence are increasing worldwide. The disease shows wide regional variations in incidence rates and etiology. HCC is particularly prevalent in Asian countries relative to Western countries. Over 80% of HCC cases occur in Africa and Asia. China alone accounts for more than 50% of cases worldwide.^{4,5} Age-standardized (world) incidence rates in South-Eastern to Eastern Asia range from 21.0 to 26.8 per 100,000, distinctly higher than the rates in Northern Europe (EU) and North America, which range from 6.6 to 10.1 per 100,000. Age-standardized (world) mortality rates are similarly much higher in South and North Eastern Asia (17.2 to 34.0 per 100,000) than in Northern EU and North America (3.1 to 4.4 per 100,000).⁶

Virtually any cause of liver damage that leads to cirrhosis can predispose an individual to HCC. The main risk factors for primary liver cancer (PLC) are chronic infection with hepatitis B virus (HBV) or hepatitis C virus (HCV), aflatoxin B1-contaminated foodstuffs, heavy alcohol intake, obesity, and type 2 diabetes mellitus.⁷ Once cirrhosis is established, the annual incidence of HCC is 3% to 5% and one-third of these individuals will develop HCC over their lifetime.⁸ Most cases of HCC arise in eastern Asia and sub-Saharan Africa, where the dominant risk factor is chronic HBV infection, together with exposure to aflatoxin B1.⁹ In contrast, in North America, EU, and Japan, HCV infection is the main risk factor, together with alcohol use.¹⁰

Intermediate-stage HCC patients belong to the Barcelona Clinic Liver Cancer (BCLC) Stage B. The stage consists of patients with preserved liver function and performance status who are not eligible for curative treatments, such as surgery and liver transplantation. It includes a heterogeneous patient population that presents with a wide range of tumor extension and liver function (Child-Pugh compensated A5 cirrhosis to decompensated B9).¹¹

Chemoembolization is recommended for the treatment of intermediate-stage HCC (BCLC Stage B). Transcatheter arterial therapies for HCC were first described in the 1970s¹² and include a variety of techniques (eg, TACE, bland embolization, trans-arterial embolization [TAE]). The use of TACE was adopted into practice guidelines based on 2 meta-analyses^{13,14} and 2 seminal placebo-controlled randomized clinical trials (RCTs)^{15,16} published in 2002. TACE has since been widely used, with conventional TACE being the most widely practiced embolotherapy for HCC.¹² The largest global HCC observational study (GIDEON) suggests that nearly half of all HCC patients receive TACE at some timepoint in the course of the disease.¹⁷ Real-world data and clinical experience demonstrate TACE to be the method of choice for the treatment of intermediate-stage HCC, applied in about 50% to 60% of patients.^{18,19}

However, TACE is considered a palliative treatment. Significant tumor response is achieved in 17-61.9% in individuals administered TACE, but TACE often fails to induce complete necrosis of the lesion. Even in cases where complete ablation is achieved, tumors commonly recur post-TACE

and repeated TACE treatments are usually required.²⁰ In the GIDEON study, 59.5% of patients received 2 or more TACE sessions.¹⁷ Across different TACE studies, the majority of participants have received > 1 TACE session.^{15,16,19,21,22,23,24,25,26}

In addition, TACE damages normal liver cells. Variable degrees of liver function impairment are observed post-TACE. The most common adverse effects of TACE include signs of liver injury and hepatic insufficiency. Elevated aminotransferases and negative changes in liver function tests (LFTs) are seen in almost all patients.^{27,28} The impact of treatment on liver function is problematic, particularly for patients who undergo repeated TACE sessions. The majority of patients with HCCs have underlying cirrhosis and preserving liver function is important. Physicians have to consider the risks of TACE and avoid adverse effects that will outweigh survival benefit. These have led to efforts to define when continuing TACE will be an ineffective therapeutic option.^{20,29,30}

The palliative nature of TACE and the need for a safer alternative for better liver function preservation has driven efforts to improve outcomes with TACE in patients with intermediate-stage HCC. Over the past decade, significant effort has been focused on clinical trials combining TACE with systemic therapies, including sorafenib, brivanib, and orantinib.³¹ To date, these studies have been unsuccessful.

Despite these failures, the research on TACE is still ongoing. In particular, deeper investigation into combination strategies is recommended.³² The avidity with which this effort is pursued is reflected in the number of ongoing TACE studies. There are currently over 100 studies registered on ClinicalTrials.gov exploring combinations of TACE with systemic agents, including immunotherapy.³³ At present, however, TACE remains the sole recommended treatment for intermediate-stage HCC. No systemic agent has been successfully developed for this stage of the disease.

